7.6.2.6 Exploratory Efficacy Analysis

X-rays will be obtained at Baseline and Weeks 12, 24, 36, 48, 72, 96, 120, 144, and every 24 weeks as applicable through the EoT Visit, or until fractures/pseudofractures are healed. The last assessment for each subject prior to receiving KRN23 will be used as Baseline.

Assessments of PROs will be measured at Baseline and Weeks 12, 24, 36, 48, 72, 96, 120, and 144. Subjects will not be required to complete the BPI and SF-36 past Week 144. The last assessment for each subject prior to taking KRN23 will be used as Baseline.

Assessments of physical function will be measured at Baseline, Weeks, 24, 36, 48, and 72. The last assessment for each subject prior to taking KRN23 will be used as Baseline.

The mean CFB will be described across subjects in terms of the mean and SD and will be tested using the generalized estimating equation (GEE) method. The model for change from Baseline will include Baseline and time as a categorical variable.

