#### 3.3 Randomization and Blinding Method of Assigning Subjects to Treatment Groups

All subjects received KRN23 on an open-label basis. Randomization and blinding are not applicable in this study.

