## 8 STATISTICAL METHODS OF ANALYSIS

### 8.1 General Principles

The statistical analyses will be reported using summary tables, figures, and data listings. Statistical tests will be 2-sided at the alpha=0.05 significance level and 2-sided 95% confidence interval will be used. All p-values will be presented as nominal p-values. No adjustment on multiplicity will be made. Continuous variables will be summarized with means, standard deviations, standard errors, medians, Q1, Q3, minimums, and maximums. Categorical variables will be summarized by counts and by percentages of subjects in corresponding categories. No imputation on missing data will be made, unless stated otherwise. All data obtained from the CRFs as well as any derived data will be included in data listings.

The Week 24 analysis will be performed when all patients enrolled in the study have completed the Week 24 visit or have discontinued the study. The final analysis will be conducted when all patients enrolled in the study have completed the Week 72 visit or have discontinued the study.

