#### 8.1.1 Repeated Measure Model: General Estimating Equations

When the sample size and number of observations allow it, the change from baseline over time and the binary endpoints over time will be analyzed using a generalized estimation equation (GEE) model that includes time as the categorical variable and adjusted for baseline measurement. The covariance structure that will be used for the GEE model is compound symmetry which specifies constant variance for the assessments and constant covariance between the assessments over time. If the compound symmetry covariance structure leads to non-convergence, Quasi-Likelihood Information Criterion (QIC) will be used to select the best covariance structure. Model based estimates of the changes from baseline and corresponding 95% confidence intervals will also be provided along with p-values for assessing statistical significance.

The p-value for testing the statistical significance of the change from the baseline to week 24 (for the interim analysis) and to week 72 (for the final analysis) assessments will be provided for changes from baseline in primary PD endpoints, selected safety endpoints (eGFR, creatinine, amylase), PRO endpoints (BPI, WOMAC, SF-36) and clinical outcomes endpoints (6MWT, percent predicted 6MWT, TUG).

For week 24 analysis, only measurements up to week 24 will be included in the model. For final analysis (week 72), all measurements will be included in the model.

If the number of observations are insufficient for analyses using a GEE model, a descriptive summary will be provided, and analyses using observations at a single time point, such as paired t-test or nonparametric methodologies, will be considered.

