### **8.1.2 Graphic Displays and Study Results**

Graphical displays of study endpoints will be completed and include both observed study data and modeled analyses, where applicable. Arithmetic means, least square means (where applicable), and appropriate measure of dispersion (e.g., standard deviation, standard error) or confidence intervals may be displayed in figures. In general, graphical displays will accompany each planned analysis to present study results.

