## 8.8 Endpoints

### 8.8.1 Pharmacodynamic Endpoints

The number and proportion of subjects with serum phosphorus level in the normal range ( $\geq 2.5$  and  $< 4.5$ ) at each time point will be provided, along with the two-sided 95% confidence intervals, obtained using the GEE model described in Section 8.1.1. An overall summary of the number and proportion of patients who ever reached the normal range over the duration of the study will also be provided. Additional analyses of serum phosphorus including observed values, change from baseline, percent change from baseline over time will be summarized.

For the final analysis, the primary PD endpoints at all post-baseline visits will be compared to baseline using the GEE model described in Section 8.1.1, and the primary statistical comparison will be between the levels at baseline and week 72.

For the interim analysis, the primary PD endpoints at all post-baseline visits prior or at week 24 for all patients will be compared to baseline using the GEE model, and the primary statistical comparison will be between the levels at baseline and week 24.

For all primary PD endpoints descriptive statistics of observed values and of changes from baseline at each visit will be provided.

Graphs showing the change over time in key PD parameter for both observed measure and the change from baseline will be provided. The relationship between various PD parameters as well as KRN23 concentrations may be examined.

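### In this single-arm study, the baseline-adjusted GEE for change from baseline generally gives intervals that are too narrow if mean change is evaluated at the observed mean baseline and change depends on baseline

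*SAP*

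**What the plan says.** SAP 8.1.1 analyses change from baseline over time with "a generalized estimation equation (GEE) model that includes time as the categorical variable and adjusted for baseline measurement". Protocol 7.6.2.6 agrees: "The model for change from Baseline will include Baseline and time as a categorical variable".

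On the covariance, SAP 8.1.1 states: "The covariance structure that will be used for the GEE model is compound symmetry". On the output, it states: "Model based estimates of the changes from baseline and corresponding 95% confidence intervals will also be provided along with p-values". The p-values apply to the primary PD endpoints, eGFR, creatinine, amylase, BPI, WOMAC, SF-36, 6MWT and TUG. For the primary PD endpoints in the final analysis, SAP 8.8.1 adds that "the primary statistical comparison will be between the levels at baseline and week 72". SAP 8.1 sets the standard: "Statistical tests will be 2-sided at the alpha=0.05 significance level and 2-sided 95% confidence interval will be used".

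There is one group only. SAP 3.3: "All subjects received KRN23 on an open-label basis".

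Three things are left open:
- **Evaluation point.** Neither document gives the baseline value at which the mean change is evaluated. SAP 8.1.2 mentions least-squares means, for figures and only where they apply.
- **Standard error.** Neither says whether it is empirical (sandwich) or model-based.
- **Mean baseline.** Neither plans to carry its sampling variability into the interval, whether by an added variance term, a bootstrap, or a model with baseline as an outcome.

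**The concern.** Adjusting change for baseline is good practice in a randomised trial: a chance high or low baseline is shared by the arms and cancels from their difference. Here nothing cancels. The estimate is the mean change itself, and the mean baseline of about 20 subjects is a random draw. A sample that happens to start high tends to drift back, and the adjusted model counts that drift as precisely estimated change.

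At stake is whether a nominal 95% interval or 5% test for a continuous endpoint performs as SAP 8.1 states. It matters most for borderline results on the patient-reported, functional and renal measures.

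**Working it through.** The documents give no power, precision, SD or correlation figure, so there is nothing of theirs to reproduce. Their only nominal values are two-sided alpha 0.05 and 95% intervals (SAP 8.1), so the critical value is 1.960.

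**Inputs**
- From the documents: one arm; change-score GEE with baseline and categorical visit; 20 subjects (protocol synopsis; SAP 3.5 says about 25).
- Assumed: correlation r between baseline and a visit; ratio k of the follow-up SD to the baseline SD; mean change evaluated at the observed mean baseline.

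**Closed form** (complete data, baseline variance set to 1)
1. The adjusted mean at the observed mean baseline equals the raw mean change.
2. Slope of change on baseline: g = rk − 1.
3. Variance of change: V = 1 + k² − 2rk.
4. Variance of change given baseline: R = k²(1 − r²) = V − g².
5. The reported squared SE tends to R/n. The true one is V/n. The omitted term is g²·Var(baseline)/n.
6. SE ratio, reported over true: √(R/V). It does not contain n.
7. Actual alpha: 2·[1 − Φ(1.960 × ratio)].

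**Equal SDs (k = 1).** The ratio becomes √((1 + r)/2).

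| r | SE ratio | Type I error | Coverage | Widening needed (1/ratio) |
|---|---|---|---|---|
| 0.3 | √0.65 = 0.806 | 11.4% | 88.6% | 24% |
| 0.5 | √0.75 = 0.866 | 9.0% | 91.0% | 15% |
| 0.7 | √0.85 = 0.922 | 7.1% | 92.9% | 8% |
| 0.8 | √0.90 = 0.949 | 6.3% | 93.7% | 5% |

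**Unequal SDs, r = 0.5**
- k = 0.7: R = 0.3675, V = 0.79, ratio 0.682, alpha 18.1%.
- k = 1.5: R = 1.6875, V = 1.75, ratio 0.982, alpha 5.4%.
- k = 2: g = 0, ratio 1, alpha 5.0%.

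**Simulation** (no true change, baseline plus 5 visits, equal SDs; type I error at r = 0.3 / 0.5 / 0.7 / 0.9)

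| n | Adjusted, sandwich SE, normal reference | Adjusted, residual df, t reference | Paired t |
|---|---|---|---|
| 20 | 14.5 / 11.9 / 10.2 / 8.3% | 10.2 / 8.1 / 6.6 / 5.4% | 5.1 to 5.2% |
| 100 | 12.0 / 9.5 / 7.8 / 6.2% | 11.1 / 8.7 / 7.2 / 5.6% | 5.0 to 5.1% |
| 1000 | 11.5 / 9.5 / 6.4 / 5.2% | 11.4 / 9.4 / 6.3 / 5.1% | 4.5 to 5.5% |

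The n = 1000 row rests on 5,000 runs. At n = 20 the sandwich column also carries ordinary small-sample bias: it reads 7.5% when the slope is zero. The t-reference column removes that part and the excess remains. A standard GEE routine at n = 300 and r = 0.5 gave an empirical SD of 0.059 against a mean SE of 0.050, whether robust, model-based or bias-reduced. The choice among these SEs does not cure the fault.

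**Check on the remedy.** Entering baseline as the time-0 response recovers the right mean change, but its SE must be chosen with care.
- *Model-based SE under compound symmetry.* This is wrong if baseline correlates less with the visits than the visits do with each other. With correlations 0.3 and 0.7 and 5 visits, the pooled correlation is (5 × 0.3 + 10 × 0.7)/15 = 0.567. The SE ratio is √(0.433/0.7) = 0.787 and alpha is about 12%. With 0.5 and 0.7, the pooled value is 0.633, the ratio √(0.367/0.5) = 0.856, and alpha about 9%. Neither depends on n.
- *Sandwich SE with a normal reference, n = 20.* Rejection is P(|t₁₉| > 1.960 × √(19/20) = 1.910) = 7.1%.

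**The case against.** **The interval is valid given the observed baselines.** This stands as a statement about conditional inference. The cohort is also a small group drawn from two earlier studies and sized by availability. But the SAP presents the result as a test of change from baseline, without that condition, and readers will take it as mean change in adults with XLH.

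**The study is exploratory and the p-values nominal.** SAP 3.5 and 8.1 say so. SAP 8.8.1 and 8.8.2.3 also plan observed changes by visit for the PD endpoints and 6MWT, and SAP 8.1 includes standard errors among the summaries, so an unadjusted SE will be available there. This lowers the weight. It does not make a nominal 95% interval cover 95%, and SAP 3.6 foresees Week 24 results supporting regulatory filings.

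**The size is unknown.** This stands. Nothing in the documents fixes r or k. At r = 0.7 to 0.8 with equal SDs, the excess is only 2.1 to 1.3 points of alpha. Equal SDs are doubtful for FGF23, which protocol 5.3 says rises on treatment.

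**A reader might infer that every interval from this model is too narrow at any sample size.** The documents do not support that. The evaluation point is not stated, and the shortfall vanishes when change is unrelated to baseline. Because the model has one common baseline slope, the interval at a single visit could even be too wide if that visit's own slope had the opposite sign.

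**A reader might also infer that 6MWT, TUG and bone markers get two conflicting analyses.** They do not: SAP 8.8.2.3, 8.8.2.4 and Appendix 1 use a paired t-test in the Week 24 analysis and the GEE in the Week 72 analysis. The SEs rest on different footings, but at different timepoints.

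**Conclusion.** The concern holds with two conditions: mean change is evaluated at the observed mean baseline treated as fixed, and change is related to baseline. Measurement error and regression to the mean make the second likely. Under both, the intervals and tests for continuous endpoints are generally too favourable, by an amount that does not shrink with n.

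With equal SDs, the excess over 5% runs from 1.3 points (r = 0.8) to 6.4 points (r = 0.3). It is larger if the follow-up SD is below the baseline SD, and at moderate r nearly absent if it is well above. All of this rests on assumed values of r and k.

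It would go too far to call the serum phosphorus conclusion unsafe: a large effect is little affected. The GEE analyses of binary endpoints (responders, phosphorus in the normal range) are outside this point. The change should be made, because the specified model gives error bars that do not match their label and the repair is cheap.

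**What to change.** For continuous endpoints in SAP 8.1.1 and protocol 7.6.2.6, drop the baseline covariate. Then either:
- fit the GEE to change scores with visit only; or
- enter baseline as the time-0 response and estimate each change as visit minus time 0.

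In both cases name the SE and the reference: empirical (sandwich) SE with a small-sample correction, and a t distribution with n − 1 degrees of freedom. Do not use model-based compound-symmetry SEs. With complete data, and the n/(n − 1) correction to the variance, this gives the paired-t result.

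Alternatively, keep the adjusted model, state that it is evaluated at the observed mean baseline, and add g²·s²(baseline)/n to the squared SE, with a t reference. In simulation at n = 20 this gave type I error of 4.3% to 4.6%. It relies on the common slope fitting each visit.

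Cost: a few sentences of SAP and protocol wording and a small program change. With equal SDs, intervals widen by about 5% (r = 0.8) to 24% (r = 0.3).

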### **8.1.2 Graphic Displays and Study Results**

Graphical displays of study endpoints will be completed and include both observed study data and modeled analyses, where applicable. Arithmetic means, least square means (where applicable), and appropriate measure of dispersion (e.g., standard deviation, standard error) or confidence intervals may be displayed in figures. In general, graphical displays will accompany each planned analysis to present study results.

### **8.1.3 Direction of Effects for the PRO Endpoints**

The three PRO endpoints for the study are not scaled in the same directions. In the SF-36v2 a higher score indicated better health whereas in the BPI and WOMAC higher scores indicate worse health. They are presented as-is, with reminders that improvements in health appear as positive numbers for the SF-36v2 and BPI scales and as negative numbers for the WOMAC scales.

## **8.2 Demographics and Baseline Characteristics**

Summaries of demographic characteristics will include descriptive statistics for age, height, weight, BMI, renal ultrasound scores, baseline skeletal survey radiographs measures (mean, standard deviation, median, minimum and maximum values) and for sex, race, ethnicity, PHEX mutation, radiograph location (number and percentage of subjects in each category).

## **8.3 Disease Characteristics and Medical History**

### **8.3.1 Medical History / XLH Medical History**

Medical history will be summarized by body system and will also be listed by subject.

### **8.3.2 XLH Treatment History**

A summary of subjects' past XLH treatment with oral phosphate (e.g., K-Phos, Phospha, Phosphate-Sandoz) and vitamin D metabolite (e.g. Calcitriol, Rocaltrol, alfacalcidol, Alpha-calcidol/1,alpha, 1,25 Vitamin D3, dihydrotachysterol) therapy will be presented. Use of calcimimetics or the treatment of hyperparathyroidism will also be reported. For subjects receiving standard of care therapy for XLH (phosphate and/or vitamin D) the drug name, duration of treatment, dose and frequency of administration will be listed. A summary of currently used walking devices will be included.

## **8.4 Subject Accountability**

Subject disposition summaries will include the number of subjects who received study medication, the number of subjects who completing the study, and the reasons for study discontinuation. The number of subjects included in the safety, pharmacodynamics and efficacy analysis, respectively, will be presented.

## 8.5 Dosing Summary

The total dose administered, weight-based dose will be summarized by study visit for the Safety Population. Study medication dispensing and treatment compliance will be summarized in individual subject listings.

## 8.6 General Safety

All safety analyses will be performed on the safety analysis set, unless stated otherwise. General safety will include AEs, treatment related AEs, SAEs, AE of injection site reaction (grouped by High-Level Group Term), laboratory measurements including chemistry, hematology, and urinalysis parameters, GFR, amylase, HAHA, concomitant medications, physical exams, pregnancy test and vital signs. No hypothesis testing is planned for safety data.

### 8.6.1 Adverse Events

Reported adverse event (AE) terms are coded to MedDRA (version 18.1). All reported events will appear in AE listings, however only TEAE will be summarized. TEAEs are defined as AEs with onset on or after the time of initiation of study drug administration.

The following AEs will be summarized:

- All TEAEs
- Related TEAEs
- Events to monitor:
  - Injection site reactions
  - Gastrointestinal events
  - Immunogenicity
  - Ectopic mineralization
  - Hyperphosphatemia
  - Restless legs syndrome
- Grade 3/4 TEAEs
- Serious TEAEs
- Serious related TEAEs
- TEAEs resulting in discontinuation
- Fatal TEAEs.

Summaries of TEAEs will show incidence rates for each MedDRA primary SOC and PT.

All TEAEs will be tabulated in the following manner: by system organ class/preferred term in descending order, by system organ class/preferred term/relationship to study drug, and by system organ class/preferred term/severity. Additionally, treatment-emergent SAEs and TEAEs related to investigational drug will be tabulated by system organ class/preferred term in descending order.

Injection site reactions (ISR) will be listed for PT, seriousness, severity, outcome, relationship to study drug, and onset time from investigational product administration.

### **8.6.2 Safety Lab Parameters**

The descriptive statistics will be provided for lab safety parameters (chemistry, hematology, and urinalysis parameters, GFR, HAHA). In addition, shift tables will be provided for HAHA (with categories Yes/No) and for amylase. For amylase, the following categories will be used:

- Normal
- Grade 1: 1 - 1.5 x ULR
- Grade 2: 1.5 – 2 x ULR
- Grade 3: 2 – 5 x ULR
- Grade 4: > 5 x ULR.

### **8.6.3 Concomitant Medications**

Each medication will be coded to a preferred name and an Anatomic Therapeutic Classification (ATC) code using WHODrug. The number and percentage of subjects taking each concomitant medication will be displayed by preferred name. This display will be created for the safety analysis set. A concomitant medication listing will also be made. Prior medications, i.e. medications that were used within 30 days before the Screening visit will also be listed.

### **8.6.4 Physical Examination**

Physical exam results will include the assessment of general appearance; head, eyes, ears, nose, and throat (HEENT); the cardiovascular, dermatology, lymphatic, respiratory, gastrointestinal, musculoskeletal, genitourinary, neurological systems All physical examination assessments will be listed.

### **8.6.5 Pregnancy Test**

Subject level listing for pregnancy test results will be created for those who had positive pregnancy test.

### **8.6.6 Vital Signs**

Systolic blood pressure, diastolic blood pressure and heart rate etc. and their changes from baseline over time will be summarized by descriptive statistics including mean, standard error etc. Individual subject listing of vital signs will be provided.

### **8.7 Ectopic Mineralization Safety**

Ectopic mineralization safety data includes renal ultrasound, ECG, ECHO, serum calcium, creatinine, GFR, iPTH, 24-hr urinary calcium excretion rate, fasting 2-hr urinary calcium/creatinine. The observed values and changes from baseline in the ectopic mineralization safety data will be summarized and listed by individual subjects.

#### **8.7.1 Renal Ultrasound**

Renal ultrasound will be conducted with findings of nephrocalcinosis graded on a 5-point scale and by a central reader. These results will be summarized by time point. Furthermore, a grade shift table summarizing changes from baseline by time point will also be created.

The number and percentage of subjects with nephrolithiasis observed in the kidney will be summarized by time point. A shift table summarizing changes from baseline by time point will be created.

A listing of renal ultrasound nephrocalcinosis scores, the presence or absence of nephrolithiasis in the kidney and the radiologist's comments will also be provided.

#### **8.7.2 ECG**

Descriptive statistics for the absolute measurements and changes from Baseline for selected ECG parameters will be reported. These include the following intervals: QT, QT corrected for heart rate, the time elapsed from the onset of atrial depolarization to the onset of ventricular depolarization (PR), and time elapsed for depolarization of the ventricles (QRS).

The frequency of subjects with a maximum increase from Baseline in the QTc interval will be summarized according to the following categories: >30 ms and >60 ms. In addition, the frequency of subjects with QTc post dose values according to the following categories: >450 ms, >480 ms and >500 ms, will be summarized.

A listing of all ECG parameters including the overall assessment will also be created.

#### **8.7.3 ECHO**

ECHO data will be centrally read to assess for evidence of ectopic mineralization in the heart and aorta and to evaluate for signs of LVH or cardiac dysfunction. Descriptive statistics for the various continuous ECHO measurements (e.g., left ventricular mass index, etc.) will be at the scheduled time points and will include the change from baseline value. The summary of

the descriptive statistics will be displayed by visit. Shift tables will be provided for categorical ECHO measurements (e.g. ectopic mineralization score, aortic and mitral valve regurgitation). A listing of all ECHO parameters will be provided.

## 8.8 Endpoints

### 8.8.1 Pharmacodynamic Endpoints

The number and proportion of subjects with serum phosphorus level in the normal range ( $\geq 2.5$  and  $< 4.5$ ) at each time point will be provided, along with the two-sided 95% confidence intervals, obtained using the GEE model described in Section 8.1.1. An overall summary of the number and proportion of patients who ever reached the normal range over the duration of the study will also be provided. Additional analyses of serum phosphorus including observed values, change from baseline, percent change from baseline over time will be summarized.

For the final analysis, the primary PD endpoints at all post-baseline visits will be compared to baseline using the GEE model described in Section 8.1.1, and the primary statistical comparison will be between the levels at baseline and week 72.

For the interim analysis, the primary PD endpoints at all post-baseline visits prior or at week 24 for all patients will be compared to baseline using the GEE model, and the primary statistical comparison will be between the levels at baseline and week 24.

For all primary PD endpoints descriptive statistics of observed values and of changes from baseline at each visit will be provided.

Graphs showing the change over time in key PD parameter for both observed measure and the change from baseline will be provided. The relationship between various PD parameters as well as KRN23 concentrations may be examined.

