7.6.1.2 Primary Pharmacodynamic Endpoints

Pharmacodynamic parameters will be summarized at Baseline and at each observed time that they are collected. The following endpoints will be examined:

- Number and percentage of subjects who have serum phosphorus levels which, at any time after dosing are in the normal range: ≥ 2.5 and ≤ 4.5 mg/dL
- Change from baseline in serum biochemistry parameters associated with XLH, as measured by serum phosphorus, iPTH, FGF23, and 1,25(OH)₂D
- Change from baseline in urinalysis parameters associated with XLH, as measured by 2-hour urine TmP/GFR and TRP, i.e., calcium, creatinine, and phosphorus
- Change from baseline in urine parameters associated with XLH, as measured by 24-hour urine, i.e., urinary phosphate, calcium, creatinine, and urine calcium/creatinine ratio
- Change from baseline in bone biomarkers associated with XLH, as measured by total ALP and BALP, CTx, and P1NP
- Change from baseline in fractional excretion of phosphorus (FEP), defined as $100\% \times (2\text{-hour urine phosphorus} \times \text{serum creatinine}) / (2\text{-hour urine creatinine} \times \text{serum phosphorus})$

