7.6.2.5 Pharmacodynamic Analyses

Pharmacodynamic parameters will be summarized at Baseline and at each observed time that they are collected. Correlations among PD parameters may also be assessed.

The number and percent of subjects who achieved the normal target range of serum phosphorus (≥ 2.5 and ≤ 4.5 mg/dL).

Individual PD-time plots may be presented for each subject as well as mean PD-time plots. Additional analyses using statistical models may be performed. The relationship between various PD parameters as well as KRN23 concentrations may be examined.

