## 2 STUDY OBJECTIVES

### 2.1 Primary Safety and Pharmacodynamics

The primary objectives of this study are to:

- Assess the long-term safety of KRN23 SC administration in adult subjects with XLH
- Assess the proportion of subjects achieving serum phosphorus levels in the normal range (2.5-4.5 mg/dL) with long-term administration of KRN23
- Assess long-term PD of KRN23 as measured by changes in the following:
  - Serum and urinary phosphorus
  - TmP/GFR and TRP
  - Serum 1,25(OH)2D
  - Serum FGF23
  - Bone biomarkers: serum ALP, bone-specific ALP (BALP), carboxy terminal cross-linked telopeptide of type I collagen (CTX), and procollagen type 1 N-terminal propeptide (P1NP)
- Assess long-term immunogenicity of KRN23 as measured by presence of anti-KRN23 antibody (HaHa)

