### 4.2 Pharmacodynamics Endpoints

The primary pharmacodynamics endpoints are:

- Number and percentage of subjects who have serum phosphorus levels which, at any time after dosing are in the normal range ( $\geq 2.5$  and  $\leq 4.5$ ) or outside the normal range
- Change from baseline in serum biochemistry parameters associated with XLH, as measured by serum phosphorus, iPTH, FGF23 (total and free), and  $1,25(\text{OH})_2\text{D}$
- Change from baseline in urinalysis parameters associated with XLH, as measured by 2-hour urine TmP/GFR and TRP, i.e., calcium, creatinine, and phosphorus
- Change from baseline in urine parameters associated with XLH, as measured by 24-hour urine, i.e., urinary phosphate, calcium, creatinine, and urine calcium/creatinine ratio
- Change from baseline in bone biomarkers associated with XLH, as measured by total ALP and BALP, CTx, and P1NP
- Change from baseline in fractional excretion of phosphorus (FEP), defined as  $100\% * (2\text{-hour urine phosphorus} * \text{serum creatinine}) / (2\text{-hour urine creatinine} * \text{serum phosphorus})$

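### SAP 8.8.1 analyses the normal-phosphorus endpoint with an upper limit of <4.5, although SAP 4.2 and the protocol define it as ≤4.5 mg/dL; the expected effect is small

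*SAP*

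**What the plan says.** The measure is the first-listed primary pharmacodynamic endpoint. Its normal range is stated in these places:

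- **SAP 8.8.1**, the section that specifies the analysis: "in the normal range ( $\geq 2.5$ and $< 4.5$ ) at each time point will be provided".
- **SAP 4.2**, the endpoint list: "in the normal range ( $\geq 2.5$ and $\leq 4.5$ ) or outside the normal range".
- **Protocol 7.6.1.2**, the primary pharmacodynamic endpoints: "at any time after dosing are in the normal range: ≥ 2.5 and ≤ 4.5 mg/dL".
- **Protocol 7.6.2.5**, the pharmacodynamic analyses: "achieved the normal target range of serum phosphorus (≥ 2.5 and ≤ 4.5 mg/dL".
- **SAP 2.1**, the primary objective: "serum phosphorus levels in the normal range (2.5-4.5 mg/dL". This gives the unit but does not say whether the limits are included.

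SAP 3.1 and protocol 7.1 also give the ULN as 4.5 mg/dL, and both use a level above it as the out-of-range condition.

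SAP 8.8.1 plans two outputs. One is the by-visit result, described as "The number and proportion of subjects with serum phosphorus level in the normal range", with 95% confidence intervals from the GEE model of SAP 8.1.1. The other is an overall count of subjects who ever reached the normal range. The second has no cut-off of its own, so it takes the one stated in the same paragraph.

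**The concern.** A programmer works from SAP 8.8.1, and there a reading equal to the ULN is not normal. The endpoint definition in SAP 4.2 and in the protocol says that it is. Neither document explains the strict inequality or says which statement takes precedence.

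At stake is whether the reported result matches the endpoint as defined. SAP 4.2 also asks for the number of subjects outside the range. Under the 8.8.1 rule a reading of 4.5 falls outside, and since it is not below 2.5 it could only be shown as high, although it does not exceed the ULN. If the mismatch is found after database lock, someone must choose between the two rules with the data in view.

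**Working it through.** The plan gives no figure to reproduce on this point. The check sets the statements side by side and then sizes the effect under stated assumptions.

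**1. The statements compared**

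| Place | Lower limit | Upper limit | Is 4.5 normal? |
|---|---|---|---|
| SAP 8.8.1 | ≥2.5 | <4.5 | No |
| SAP 4.2 | ≥2.5 | ≤4.5 | Yes |
| Protocol 7.6.1.2 | ≥2.5 | ≤4.5 mg/dL | Yes |
| Protocol 7.6.2.5 | ≥2.5 | ≤4.5 mg/dL | Yes |
| SAP 2.1 | 2.5 | 4.5 mg/dL | Not stated |

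The lower limit and the number 4.5 agree throughout. Only the inclusion of 4.5 differs. Applying both rules to every value from 1.0 to 6.9 mg/dL in steps of 0.1 gives one value that is classified differently: 4.5.

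**2. Inputs for the size**

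- Subjects: 20 (protocol synopsis and 7.6.4); approximately 25 in SAP 3.5.
- Post-baseline serum phosphorus time points to Week 72: 17 (SAP Appendix 1: Weeks 2, 4, 6, 8, 10, 12, 24, 26, 28, 36, 38, 40, 48, 50, 52, 60, 72).
- Samples: 20 × 17 = 340.
- Assumed, not in the documents: reporting to 0.1 mg/dL, normally distributed values, and the means and SDs below.

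**3. Chance that a sample reads exactly 4.5**

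Formula: p = Φ((4.55 − mean)/SD) − Φ((4.45 − mean)/SD). For mean 3.0 and SD 0.6: Φ(2.583) − Φ(2.417) = 0.99511 − 0.99217 = 0.0029.

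| Mean | SD | p | 340 × p |
|---|---|---|---|
| 2.5 | 0.5 | 0.003% | 0.01 |
| 2.5 | 0.6 | 0.03% | 0.1 |
| 3.0 | 0.5 | 0.09% | 0.3 |
| 3.0 | 0.6 | 0.29% | 1.0 |
| 3.0 | 0.7 | 0.58% | 2.0 |
| 3.5 | 0.5 | 1.09% | 3.7 |
| 3.5 | 0.6 | 1.66% | 5.6 |
| 3.5 | 0.7 | 2.06% | 7.0 |

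**4. Effect at a single visit**

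One reclassified subject moves the proportion by 100/20 = 5 percentage points, or 100/25 = 4 points. The expected number per visit among 20 subjects is 20 × p. That is about 0.06 at mean 3.0 and SD 0.6, and 0.41 at mean 3.5 and SD 0.7. The chance of at least one, 1 − (1 − p)^20, is about 6% and 34% in those two cases.

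**5. How well the higher scenarios fit the documents**

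With mean 3.5, the share of samples reading above 4.5 is 1 − Φ((4.55 − 3.5)/SD). This is 4.0% at SD 0.6 and 6.7% at SD 0.7, or about 14 and 23 of 340. Protocol 7.4.5 reports that no subject exceeded 4.5 mg/dL at any time point in the dose-escalation study, and it gives 2.5 to 3.5 mg/dL as this study's target fasting peak range. Eleven of the 17 time points (Weeks 4, 8, 12, 24, 28, 36, 40, 48, 52, 60 and 72) come at the end of a four-week dose interval, so they are troughs. An average of 3.5 over all samples is therefore hard to reconcile with the documents.

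**The case against.** The strongest reply is that this is a slip of one symbol with almost no numerical consequence. Much of that stands.

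- **Two results in the study report.** A reader might infer that the report would carry two conflicting primary results. The documents do not support this. SAP 4.2 lists endpoints and plans no output of its own. Both planned outputs are in SAP 8.8.1 under one stated range. The plan as written gives one set of results under a cut-off that differs from the endpoint definition.
- **The endpoint as worded.** SAP 4.2 asks for "Number and percentage of subjects who have serum phosphorus levels which, at any time after dosing are in the normal range". A subject's status on that measure changes only if the sole in-range value, over up to 17 samples to Week 72, is exactly 4.5. Any value of at least 2.5 and below 4.5 qualifies under both rules.
- **The larger counts.** The 6 to 7 affected samples need an assumed mean of 3.5, which fits protocol 7.4.5 poorly.
- **Success and failure.** It is also tempting to treat 4.5 as a decision threshold. No success criterion is attached to this proportion. The study is exploratory and unpowered (SAP 3.5), and its p-values are nominal (SAP 8.1).
- **Text extraction.** A symbol misread from the PDF cannot be fully excluded, but the inclusive sign was read correctly in SAP 4.2.

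One point runs the other way. Six of the 17 time points (Weeks 2, 6, 10, 26, 38 and 50) fall two weeks after a dose. Protocol 7.2 puts the time of maximum drug concentration at 8 to 11 days, so the upper limit is more likely to be reached at these visits than at trough.

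These points limit the consequence. They do not remove the contradiction, which is in the current text of both documents.

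**Conclusion.** The point holds as a minor error: SAP 8.8.1 is wrong as written. It would count a reading of exactly 4.5 mg/dL as not normal, against the definition in SAP 4.2 and in two protocol sections, and against the ULN as both documents use it. The outputs exposed are the by-visit proportions, the binary GEE model and, rarely, the count of subjects who ever reached the range.

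The expected size is about 0 to 1 of 340 samples to Week 72. This rests on reporting to 0.1 mg/dL, normally distributed values, a mean of 2.5 to 3.0 mg/dL and an SD of 0.5 to 0.6, none of which the documents give. Nothing suggests that the strict inequality was deliberate, and it is probably typographical.

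**What to change.** In SAP 8.8.1, change the upper bound from <4.5 to ≤4.5 mg/dL. The range then matches SAP 4.2 and protocol 7.6.1.2 and 7.6.2.5, and the missing unit is supplied. SAP 4.2 prints no unit either and could take the same addition. Make the change before database lock, so that the rule is not chosen with the data in view.

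The cost is one symbol and a unit. Only readings of exactly 4.5 change class, no other analysis is affected, and no dosing rule is touched.
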